#### Intent-to-Treat Analysis of Mortality

The primary outcome is time to death and the primary analyses will include participants in the primary treatment assessment population only. The primary and main secondary analyses of treatment effectiveness will be intention-to-treat, i.e., each participant will be included in the group in which her/his dialysis facility was randomized, regardless of adherence to the assigned strategy. The primary analysis will be performed using Cox proportional hazards model to compare the survival rates between the Intervention and usual care arms stratified by the stratification variables (see section 4.4). Variance estimation will be calculated by the robust variance estimator to adjust for clustering by facility. In secondary analyses of mortality, time by treatment interaction terms will be applied to determine whether the treatment effect on mortality varies as a function of the amount of time the patient has been on the intervention. In addition, treatment by body size and treatment by sex interaction terms will be considered to assess whether treatment effects differ by body size or gender subgroups. Multivariable Cox regression will also be used to assess the sensitivity of the results to adjustment for baseline patient and center characteristics that are not balanced between the two treatment arms and that are predictive of the death outcome.

In additional secondary analyses of mortality, each of the above analyses will be performed in the extended population including all participants in the study, as well as in the large-size subgroup of patients >42.5 L to address any indirect effects of the intervention.

#### **Analyses of Secondary Endpoints**

Several secondary analyses will be conducted, both to evaluate the secondary outcomes and to supplement the primary endpoint comparison. Secondary outcomes include hospitalization data collected during the follow-up period and quality of life measured every year. Generalized estimating equations (GEE) will be used to model repeated quality of life data. GEE can account for the correlation of repeated measures within subject and also the correlation of repeated measures within cluster. Hospitalization data will also be analyzed using a GEE approach assuming a Poisson distribution with an offset term to account for the length of follow-up for each participant.

#### Analyses Accounting for Non-Adherence

Non-adherence is one of the most common causes complicating the application of causal inference to results from randomized trials. This is particularly the case for pragmatic trials, where the biological effect of the treatment received may differ greatly from the effectiveness of the intervention as estimated using intent-to-treat analyses. While the primary statistical analyses will be performed using standard intent-to-treat approaches to estimate effectiveness, we will perform additional explanatory analyses using modern methods of causal inference to assess the biological effect of the treatment received.

There are many reasons patients may not be adherent to the study protocol. For example, patients may switch from a dialysis facility in the treatment arm to a dialysis facility in the control arm, or patients in a dialysis facility assigned to the treatment may decline to increase their treatment time. In the trial, we will collect adherence information for all participants during the entire follow-up period in the form of the length of each dialysis treatment (both prescribed and delivered) and relevant time-updated covariates (see section 4.10). Modern causal modeling methods including marginal structural models and structural nested models will be used to estimate the treatment efficacy assuming all participants are adherent to the study protocol.

#### 6.4. Managing Missing Data

Given the nature of end-stage renal disease and dialysis practices, it is possible that missing data will be above the anticipated rate of 5% per year due to transfer of care, and kidney transplantation. Extensive efforts will be made to collect complete mortality data. For example, if a patient transfers his/her care to a different dialysis facility, hospitalizations and mortality outcomes will still be collected if the dialysis facility is part of the same provider organization.

For the primary analyses of mortality, patients will be censored at the time of loss to follow-up, which can lead to bias if censoring is informative - i.e., the censoring mechanism is associated positively or negatively with survival. The major projected source of censoring is receipt of a kidney transplant, which tends to occur in healthier patients with a relatively good prognosis. The potential implications of censoring of participants who undergo kidney transplantation will be explored by estimating the cumulative incidence of both death and kidney transplantation. For the secondary quality of life outcomes, missing data may be anticipated due to death, loss to follow-up for transplant and other reasons, and dependence on participants completing the questionnaires. In secondary analyses, different strategies will be used to handle missing data due to loss-to-follow-up and death. For the former, comparisons will be made between subjects with complete follow-up and those lost to follow-up, with respect to observed characteristics, and discrepancies will be pursued to shed light on the reasons for missing data in subjects with incomplete follow-up. Inverse probability weighting (IPW) will be used when fitting GEE models. For missing data due to death, the use of statistical models based on the modern framework of principle stratification in which statistical inferences are restricted to participants who would survive in both arms (called "survivor average causal effect" (SACE) in causal inference literature) will be explored.

## 7. Data and Safety Monitoring

#### 7.1. Adverse Event Reporting

Hemodialysis sessions of 4.25 hours are not experimental procedures and there are no anticipated severe adverse effects associated with dialysis session durations of 4.25 hours compared with sessions which are shorter in duration. For this reason, the TiME Trial will not collect or report adverse events. Serious complications of hemodialysis related to technical aspects of the dialysis procedure, such as air embolism and hemolysis, are extremely rare, typically occur within the first 10-60 minutes of a dialysis session, and are not related to dialysis session duration. Further, should they occur, such events will be captured as hospitalization or death outcomes. Longer hemodialysis sessions are expected to produce gentler treatments with less fluctuation in intravascular volume. Therefore, it is anticipated that physical tolerability of dialysis sessions of 4.25 hours will be similar or better than shorter treatments.

#### 7.2. Data and Safety Monitoring Board

A Data and Safety Monitoring Board (DSMB) has been convened by the NIDDK to oversee the TiME Trial. The DSMB is comprised of individuals with expertise in dialysis, clinical trial conduct, and biostatistics. Members of the DSMB will not be involved in the conduct of the trial. The DSMB will review trial progress, data quality, and interim analyses throughout the course of the trial in accordance with a Data and Safety Monitoring Plan. The DSMB will meet regularly and make recommendations to the trial sponsor (NIH) about study progress and safety and will make recommendations about trial continuation. DSMB reports will be submitted to the IRB.

#### 7.3. Reports and Interim Analyses

The study will be monitored routinely for issues of data quality and study conduct including facility and participant enrollment and follow-up rates. Patient enrollment is expected to be completed in approximately 3 years. An interim analysis will be performed when participants reach 50% information-time. The results of these analyses will be provided to the DSMB. To avoid inflating the overall Type I error rate for the primary analysis of effectiveness, an O'Brien-Fleming boundary will be used to calculate the nominal significance level to which the interim p-value is compared. The DSMB will have the authority to recommend that the trial be stopped early based on efficacy, futility, or safety concerns. **Table 3** outlines the proposed reporting schedule.

Report	Prepared By	Provided To	Frequency	
Enrollment	DCC	SC	q 2-4 weeks	
Data Quality, Timeliness	DCC	SC, DSMB	q 3-4 mos	
Demographics (combined)	DCC	SC, DSMB	q 3-4 mos	
Interim Analysis	DCC	DSMB	12 and 24 mos	
Primary Analysis	DCC	DSMB	36 mos	
Abbreviations: DCC – Data Coordinating Center; SC – Steering Committee;				
DSMB – Data a	and Safety Monitorin	g Board		

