	
 
Unwillingness to participate. Patients receiving dialysis in facilities in the Intervention arm can participate without agreeing to a minimum dialysis session duration of 4.25 hours. Data collection for such participants will be identical to those who receive the session duration of ≥4.25 hours.
 

	

Patients who are unable to provide consent for dialysis care will be excluded from trial participation.

Outcomes	Primary Outcome: death
	Major Secondary Outcomes: hospitalizations, health-related quality of life
Duration of intervention	Up to 3 years
Analytic Approach	1. Primary outcome: intention to treat comparison of time to death between Intervention and Usual Care groups.
	Analysis will include generation of the hazard ratio and 95% confidence interval for the intervention. Significance testing will be performed with two-tailed p values of ≤ 0.05 considered significant. Survival curves with 95% confidence intervals will be generated using the Kaplan-Meier method. Secondary analyses will incorporate adjustment for covariables that are not balanced between randomization groups.

Protocol Summary		
	2.	Secondary outcomes:
		
 
a) comparison of hospitalization rates between Intervention and Usual Care groups
 

		
 
b) comparison of change over time in KDQOL™36 domains between Intervention and Usual Care groups
 

	3.	Primary analysis population : patients with anthropometric volume ≤ 42.5 liters. Referred to as "Primary Treatment Assessment Population."
	4.	Secondary analysis population: all patients. Referred to as "Extended Analysis Population."
Study Oversight	apı int	independent Data and Safety Monitoring Board (DSMB) pointed by NIH will review trial progress, data quality, and erim analyses throughout the course of the trial in accordance h a Data and Safety Monitoring Plan.

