#### 6.2.1. Revised Sample Size (incorporated June 2016)

Sample size calculations were repeated after the trial was underway to incorporate the following changes to assumptions that affect study power. These changes include the following:

- Facility enrollment did not begin until just prior to participant enrollment rather than being carried out and completed during the 12 months prior to participant enrollment. As a result the duration of participant enrollment increased from 1 year to 3 years. The duration of the trial was increased to 4.5 years to maintain a median follow-up of 2.5 years.
- 2) A total of 266 rather than 402 facilities agreed to participate and 10 facilities withdrew from the trial after randomization resulting in a smaller number of clusters and larger size of clusters.
- 3) The percentage of participants who were lost to follow-up because of transplantation or facility transfer was higher than anticipated.

4) The observed intra-cluster correlation coefficient (ICC) for mortality determined during the trial after approximately 5000 participants were enrolled was lower than anticipated with observed ICC of approximately 0.01 rather than 0.03.

**Table 2R** shows sample size requirements under scenarios that incorporate the modifications described above including enrollment period of 36 months and a total study duration of 54 months, a cluster number of 256 and cluster size standard deviation (SD) of 10 or 16, a loss to follow-up rate of 10%, and an ICC for mortality of 0.012 or 0.015. For the primary analysis, the desired detectable hazard ratio for mortality risk is 0.85 comparing the Intervention arm to the Usual Care arm in the primary treatment assessment population. A sample size of 6,880 (4250 in primary analysis population) provides 77 – 82% power to detect a HR of 0.85 with a two-sided alpha of 0.05.

Enrollment Time/Total Study Time (mos)	# Clusters	SD for Cluster Size (1° Analysis Population)	Annual Loss to F/U	Annual Mortality Rate	ICC for Mortality	Sample Size for 1° Analysis Population	Total Sample Size	Power to detect HR 0.85
12/36	402	0	5%	18%	0.03	4020	6432	80%
36/54	256	10	10%	18%	0.015	4020	6432	78%
36/54	256	16	10%	18%	0.015	4020	6432	76%
36/54	256	10	10%	18%	0.012	4020	6432	80%
36/54	256	16	10%	18%	0.012	4020	6432	78%
36/54	256	10	10%	18%	0.015	4250	6800	80%
36/54	256	16	10%	18%	0.015	4250	6800	77%
36/54	256	10	10%	18%	0.012	4250	6800	82%
36/54	256	16	10%	18%	0.012	4250	6800	80%

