#### 3.1 DSMB-Requested Interim Analysis

A mid-course interim analysis, including a futility analysis, was requested by the DSMB. The interim analysis was conducted using data through October 2016 when the information time was approximately 50%. The following plan was provided to the DSMB before the interim efficacy analysis and the futility analysis were conducted:

The TiME Trial design provides 80% power to detect a hazard ratio of 0.85 from a Cox proportional hazards model at a type 1 error rate of 5%. To account for the interim analysis of accumulated data in the TiME Trial, the Lan-DeMets alpha spending function method will be used to determine the O'Brien-Fleming boundary to maintain an overall type 1 error rate of 5%. All confidence intervals will be adjusted for the interim analysis with one-look at information time of 50% (i.e., the O'Brien-Fleming boundary for a two-sided test would be {-2.96, 2.96}). In other words, the null hypothesis that the hazard ratio equals 1 would be rejected if the test statistic is less than -2.96.

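### Protocol Table 3 was not updated for the 54-month design and contradicts the single 50%-information look, and the p ≤ 0.05 final rule in both summaries conflicts with the SAP's own 5% error commitment

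*Combined protocol and SAP*

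**What the plan says.** - **Number and timing of looks, text.** Protocol 7.3: "An interim analysis will be performed when participants reach 50% information-time". For that look, "an O'Brien-Fleming boundary will be used to calculate the nominal significance level to which the interim p-value is compared". SAP section 3 repeats this plan, and SAP 3.1 reports that the look used data through October 2016, at roughly half the information.
- **Number and timing of looks, table.** Table 3 in protocol 7.3 has an interim-analysis row at 12 and 24 months and a primary-analysis row at 36 months.
- **Trial length.** Protocol 6.2.1: "The duration of the trial was increased to 4.5 years to maintain a median follow-up of 2.5 years", and Table 2R assumes an "enrollment period of 36 months and a total study duration of 54 months". SAP 4.1 places the primary analysis after the trial is complete and queries are resolved.
- **Final test.** The Protocol Summary and the SAP's copy of it, for the primary outcome: "Significance testing will be performed with two-tailed p values of ≤ 0.05 considered significant", with a 95% confidence interval. SAP 4.1 and 4.3 specify a two-sided test but no final level.
- **Error control.** SAP 3.1: "the Lan-DeMets alpha spending function method will be used to determine the O'Brien-Fleming boundary to maintain an overall type 1 error rate of 5" per cent, and "All confidence intervals will be adjusted for the interim analysis with one-look at information time of 50" per cent. It gives the boundary as −2.96 and +2.96, then says that the null hypothesis "would be rejected if the test statistic is less than -2.96".

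**The concern.** Three things do not fit together.

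First, one section gives two monitoring schedules. The schedule in the table suits the earlier design of 12 months' enrolment and 36 months in total, not the current one. Anyone planning the database lock from Table 3 would schedule the primary mortality analysis 18 months too early, with the last patients just enrolled.

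Secondly, an interim efficacy look spends some of the 5%. If the final test still uses the full 0.05, the overall error exceeds what SAP 3.1 undertakes to hold. A primary result with p between 0.049 and 0.05 would be significant under the summaries and not significant under the SAP's spending plan.

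Thirdly, the sentence restating the interim boundary covers only the benefit side of a boundary that is given as two-sided.

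**Working it through.** **1. The plan's own interim boundary.** Inputs from SAP 3.1: Lan-DeMets O'Brien-Fleming spending, overall two-sided 5%, one look at t = 0.5.

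Spending per side is 2[1 − Φ(z₀.₀₁₂₅/√t)], with z₀.₀₁₂₅ = 2.241. At t = 0.5, 2.241/0.7071 = 3.170, so about 0.00153 is spent per side, or 0.00305 in total. The boundary is 2.963, which reproduces the stated 2.96. (The classical O'Brien-Fleming pair would be 2.797 and 1.977, so the spending version is the one in use.)

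**2. The matching final boundary.** The interim and final statistics have correlation √0.5. Solving for a total two-sided error of 0.05, given 2.963 at the look, gives a final value of 1.969: nominal p = 0.0490, about a 95.1% interval. With 1.96 at the end instead, overall alpha is 0.0510.

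The SAP says only that information was about 50%, so I repeated this at 45% and 55%. The final values are 1.965 and 1.974 (p 0.0494 and 0.0484), and overall alpha with 1.96 is 5.06% and 5.16%.

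Power cost at an 80% design: Φ(1.960 + 0.842 − 1.969) = 79.8%, a loss of about 0.2 points.

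**3. Where Table 3's months fall.** Inputs from protocol 6.2 and 6.2.1: 4,250 patients in the primary population, 18% annual mortality, 10% annual loss, HR 0.85, 36 months' enrolment, 54 months in total. Uniform accrual, equal arms and exponential times are my assumptions.

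Hazards: usual-care death −ln(0.82) = 0.1985; intervention death 0.85 × 0.1985 = 0.1687; loss −ln(0.90) = 0.1054. With death hazard λ and loss hazard μ, the chance of an observed death by follow-up f is λ/(λ+μ) × [1 − exp(−(λ+μ)f)], averaged over the accrual period.

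- Month 36 (f from 0 to 3 years): usual care 0.2246 × 2,125 = 477; intervention 0.1959 × 2,125 = 416; total 894 before rounding.
- Month 54 (f from 1.5 to 4.5 years): 0.3815 × 2,125 = 811 and 0.3373 × 2,125 = 717; total 1,527 before rounding.
- Month 54 with each participant's follow-up stopped at 3 years (protocol 4.1 and 4.9, SAP section 1): 1,421.

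| Calendar month | Expected deaths | Share of 1,527 | Share of 1,421 |
|---|---|---|---|
| 12 | 118 | 8% | 8% |
| 24 | 433 | 28% | 30% |
| 36 | 894 | 58% | 63% |

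Half the information (764 or 710 deaths) arrives near month 33, or month 32 with the cap. Neither calendar interim coincides with it. Treating 18% and 10% as hazards rather than annual risks moves the shares by less than one point.

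**4. Power at month 36.** Design effect = 1 + [(1 + CV²)m − 1] × ICC, with m = 4,250/256 = 16.6 and CV = SD/m. Table 2R's ICC of 0.012 or 0.015 and SD of 10 or 16 give 1.26 to 1.465. Power = Φ(½√(D/DE) × |ln 0.85| − 1.96), with |ln 0.85| = 0.1625.

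- Best case: 894/1.26 = 710; ½ × 26.6 × 0.1625 = 2.16; power 58%.
- Worst case: 894/1.465 = 610; ½ × 24.7 × 0.1625 = 2.01; power 52%.

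At 1,527 deaths the same formula gives 75–81%, close to the stated 77–82%. The shortfall therefore comes from the analysis date, not from my method.

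**The case against.** The best defence is that the SAP already settles the timing. SAP 3.1 describes one look at about half the information, already done, and SAP 4.1 puts the primary analysis at trial completion. Table 3 is introduced only as a proposed reporting schedule and looks like a leftover from the 36-month plan. This stands. A reader might infer that the trial would actually stop for its primary analysis at month 36; the SAP does not support that. The 52–58% describes what Table 3 would produce if followed, not what is scheduled. It remains true that no text corrects the 36-month entry, which sits under the rule that it contradicts.

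A reader might also apply ±2.96 at both calendar interims and find a larger inflation. No document does so: 2.96 is given only for one look at 50%. Lan-DeMets boundaries at 8% and 28% would be 7.96 and 4.05, and a final test at 1.96 would then give 5.00%.

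On the final level, it can be said that 0.05 in the summaries means the overall level, and that SAP 3.1 promises adjusted intervals. So it would be wrong to say that no adjustment is planned. But the summaries attach 0.05 to the p value itself, and no section gives a final critical value.

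Finally, a reader might take the one-sided sentence in SAP 3.1 to mean that a crossing towards harm has no consequence. The two-sided boundary stands in the sentence before it, and both documents let the DSMB recommend stopping for safety. Only the wording is incomplete.

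**Conclusion.** The point holds as an inconsistency in current text, in two parts of different weight.

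The larger part is Table 3. Its dates contradict protocol 7.3, SAP 3.1 and SAP 4.1, and its primary analysis would fall at about 58–63% of expected deaths, with power some 23 points below that of the full design by the same formula. The fractions rest on uniform accrual and exponential hazards at the documents' rates, and on whether follow-up is capped at 3 years.

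The smaller part is the final threshold. Against the 5% promised in SAP 3.1, a p ≤ 0.05 rule gives about 5.10% for a look at exactly 50% information. The inflation is small, but the threshold decides a borderline mortality result and should be stated once, before the final analysis. The one-sided wording in SAP 3.1 needs only clarification.

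**What to change.** 1. **Protocol 7.3, Table 3:** replace the 12- and 24-month interims with one interim at 50% information, and the 36-month primary analysis with one at trial completion (month 54).
2. **Both summaries:** replace p ≤ 0.05 and the 95% interval with the final Lan-DeMets O'Brien-Fleming boundary and its matching interval, recomputed at the actual information fraction of the October 2016 look. At exactly 50% this is |Z| ≥ 1.969, p < 0.0490, about a 95.1% interval.
3. **SAP 4.1 and 4.3:** add the same final boundary, since neither states one.
4. **SAP 3.1:** add a dated clarifying note that the stated boundary is two-sided. Leave the text itself as the record of the plan given to the DSMB before the look.

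The cost is a table correction and a few sentences, with about 0.2 points of power. No operational change is needed.

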#### Table 3. Study Reports

#### 8. **Regulatory Issues**

#### 8.1. Institutional Review Board

The University of Pennsylvania Institutional Review Board will serve as the IRB of record for the TiME Trial and provide regulatory oversight for the trial activities at the dialysis provider organizations, the dialysis facilities and the DCC.

#### 8.2. Protocol Changes

All modifications to the protocol will be approved by the Steering Committee and submitted to the IRB for approval prior to implementation. Changes will be incorporated into the protocol as amendments. The protocol changes and new versions of the protocol will be distributed to all members of the TiME Trial Study Group.

#### 8.3. Declaration of Interests

Financial and other competing interests for the investigators are documented, provided to the Institutional Review Board, updated annually, and maintained at the DCC.

#### 8.4. Data Sharing

A data sharing policy will be developed by the TiME Trial Study Group. The policy will be consistent with the data sharing policy of the NIDDK. Data that can potentially be linked to a specific participating dialysis provider organization will not be transmitted to NIH data repositories. This includes all data elements that are collected by only one of the two dialysis provider organizations and data categories with counts below a specified threshold. All PHI will be removed from any shared data sets including dates, ages >89 years and any other sparsely represented values that could potentially be identifying.

